6.2.2.1 Amgen Investigational Product: Tarlatamab

The reason for dose change of tarlatamab is to be recorded on each subject's CRFs.

Protocol Number: 20200439

Date: 05 June 2024 Page 60 of 176

6.2.2.1.1 Dosage Adjustment

Subjects should continue on the same target dose of tarlatamab (not including the initial first step dose and step doses) throughout the study with the exception of subjects who experienced a DLT or other intolerable tarlatamab-related adverse events but show evidence of clinical benefit. These subjects will have the option to reduce the dose to the immediate next lower dose level shown to be safe and tolerable in the dose exploration part of the study (Section 4.1). The study drug can be resumed once the adverse events recover to grade \leq 1, and the reintroduction of tarlatamab is deemed safe and tolerable by the investigator, Medical Monitor, and GSO. The subject must be informed of the risk of continuing on therapy. Each subject is allowed one dose reduction. For adverse events related to CRS, neurological events, and pituitary dysfunction, please see Sections 6.8.1, 6.8.3, and 6.8.4, respectively, for guidelines for dose adjustments.

If restarting tarlatamab due to adverse events, dose reductions would occur with tarlatamab (as described in Section 6.8). The study drug can be resumed once the adverse events recover to grade 0 to 1 and the reintroduction of tarlatamab is deemed safe by the investigator, Medical Monitor, and GSO.

6.2.2.1.2 Dose Delays

During the first DLT observation period, if the dosing of tarlatamab is delayed for more than 72 hours for reasons other than DLT during the DLT evaluation period, a replacement subject may be enrolled and assigned to the same dose level. The subject may continue on study only after discussion with the Medical Monitor.

After the DLT observation period, if the dosing of tarlatamab is delayed for ≤ 2 weeks, the subject should resume the treatment as soon as possible if deemed safe by the investigator. If the dosing of tarlatamab is delayed between 2 to 4 weeks due to severe or life-threatening treatment-related adverse events, the subject can resume treatment if the toxicities resolve to grade ≤ 1 or return to subjects' baseline values within 3 weeks and restarting of therapy has been deemed safe by the investigator and medical monitor.

If the dosing of tarlatamab is delayed for more than 4 weeks due to severe or life-threatening treatment-related adverse events, the subject will be discontinued from investigational product. If the dosing delay occurred under other conditions, the case will be reviewed by the sponsor to determine whether and when the subject will be allowed to resume tarlatamab.

Protocol Number: 20200439

Date: 05 June 2024 Page 61 of 176

For adverse events related to CRS, neurological events, and pituitary dysfunction, please see Sections 6.8.1, 6.8.3, and 6.8.4 respectively for guidelines for dose delays.

6.2.2.1.3 Rules for Withholding or Restarting

Tarlatamab should be withheld for any of the following:

- DLT
- Symptomatic hypophysitis (See Section 6.8.4)
- Criteria for conditional withholding of tarlatamab due to potential hepatotoxicity (Section 11.7)

Tarlatamab dosing can be resumed if the toxicities resolve to grade \leq 1 or return to subjects' baseline values within 3 weeks. The restarting of therapy should be deemed safe by the investigator and medical monitor.

Subjects should not be restarted with tarlatamab if the following treatment-related adverse events occur:

- Criteria for permanent withholding of tarlatamab due to potential hepatotoxicity (Section 11.7)
- Any grade ≥ 4 adverse events except those not considered DLT as described in Section 6.2.1.4
- Grade 3 adverse event(s) that do not recover to grade ≤ 1 within 3 weeks
- Any grade 3 adverse events that recur (with the exception of grade 3 laboratory parameters not considered clinically relevant or recurrent non-febrile grade 3 neutropenia which resolves with supportive care to grade ≤ 1 or returns to subjects' baseline values within 3 weeks)

For adverse events related to CRS, neurological events and pituitary dysfunction, please see Sections 6.8.1, 6.8.3, and 6.8.4 respectively for guidelines for dose adjustment.

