7.2 Continuation on Study Treatment After Radiologic Disease Progression

This section details the conditions necessary to allow continued treatment with tarlatamab after radiologic disease progression in subjects that continue to have clinical benefits in the investigator's judgement, provided all of the following criteria are met at each occurrence:

- Absence of threat to vital organs or critical anatomical sites (eg, respiratory failure due to tumor compression, spinal cord compression) requiring urgent alternative medical intervention with persistent immediate threat to vital organs after intervention. The presence of brain metastases may be allowed, provided the lesions are amenable to radiation therapy or dexamethasone (or corticosteroid equivalent) and the subject is clinically stable as per investigator's judgment.
- No other treatment discontinuation criteria are met.
- No significant, unacceptable, or irreversible toxicities related to any dose of the study treatment or treatment related adverse events of CTCAE grade 4 at the current dose at the time of progression.
- The subject is willing to undergo biopsy of one of the new or progressing lesions. If tumor biopsy is not clinically feasible or advisable, the subject may continue only upon agreement with the investigator and the Amgen Medical Monitor.
- Approval for continuation from the Amgen Medical Monitor.
- Palliative radiation for new, progressive, or symptomatic lesions is permitted as per Section 6.1.7. Tarlatamab must be held during treatment and radiation and must be completed at least days before the subsequent dose of tarlatamab.
- All protocol-mandated procedures must be performed as noted in the Schedule of Activities (Section 1.3) (imaging, labs, and clinic visits may be obtained earlier per clinical judgment and if clinically indicated).

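### After a recovered grade 4 DLT, Section 6.2.2.1.1 offers tarlatamab at a lower dose while Section 6.2.2.1.3 says not to restart, and neither section is said to govern

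*Protocol*

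**What the plan says.** Three consecutive protocol subsections deal with resuming tarlatamab.

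- **6.2.2.1.1 Dosage Adjustment** keeps subjects on the same target dose "with the exception of subjects who experienced a DLT or other intolerable tarlatamab-related adverse events but show evidence of clinical benefit". For that group it continues: "These subjects will have the option to reduce the dose to the immediate next lower dose level shown to be safe and tolerable". Drug can resume after recovery to grade 1 or less, provided that "the reintroduction of tarlatamab is deemed safe and tolerable by the investigator, Medical Monitor, and GSO".
- **6.2.2.1.2 Dose Delays** has a paragraph that opens "After the DLT observation period, if the dosing of tarlatamab is delayed for ≤ 2 weeks". The same paragraph says that if dosing is "delayed between 2 to 4 weeks due to severe or life-threatening treatment-related adverse events, the subject can resume treatment", on condition that the event resolves to grade 1 or baseline within 3 weeks and that the investigator and medical monitor consider restart safe. A delay of more than 4 weeks for such events means discontinuation.
- **6.2.2.1.3 Rules for Withholding or Restarting** withholds tarlatamab for a DLT, among other reasons. It allows resumption on recovery to grade 1 or baseline within 3 weeks if the investigator and medical monitor agree. It then lists treatment-related events after which subjects should not be restarted. These include "Any grade ≥ 4 adverse events except those not considered DLT as described in Section 6.2.1.4" and grade 3 events that have not recovered to grade 1 or less within 3 weeks.

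Section 6.2.1.4 defines a DLT by onset in a window after the first tarlatamab dose. It counts grade 4 events as DLTs whatever their duration, apart from listed exemptions such as short non-febrile neutropenia.

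**The concern.** A site with a subject who is benefiting, and who has recovered from a grade 4 DLT, finds an option to resume in one subsection and a bar on restart two subsections later. The choice decides whether the subject is re-exposed after a grade 4 toxicity. It also decides which SAP table the case enters: adverse events leading to discontinuation, or those leading to interruption or reduction (SAP 9.6.2). Reasons for stopping treatment (SAP 9.2) and exposure and dose modifications (SAP 9.6.8) change with it. If sites resolve the conflict differently, those tables mix two rules.

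**Working it through.** There is no figure to reproduce. The check sets the conditions side by side and asks whether one event can meet both a permission and a bar.

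| Section | Who may resume | Grade limit | Time limit for recovery | Who must agree |
|---|---|---|---|---|
| 6.2.2.1.1 | DLT or other intolerable tarlatamab-related event, with clinical benefit; lower dose level | None | None | Investigator, Medical Monitor, GSO |
| 6.2.2.1.2 | Delay of 2 to 4 weeks for severe or life-threatening related events, after the DLT observation period | None | 3 weeks | Investigator, medical monitor |
| 6.2.2.1.3 | Events for which drug was withheld, including a DLT | No restart after related grade 4 or higher, unless not considered a DLT | 3 weeks | Investigator, medical monitor |

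Four cases follow.

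1. **Treatment-related, non-exempt grade 4 event in the DLT window, recovered to grade 1 or less, clinical benefit.** It is a DLT under 6.2.1.4. Section 6.2.2.1.1 offers resumption at a lower dose. The no-restart list in 6.2.2.1.3 bars it. The sections conflict.
2. **Treatment-related grade 3 DLT that recovers after 3 weeks, clinical benefit.** Section 6.2.2.1.1 sets no time limit, so the option stands. Section 6.2.2.1.3 bars restart. The sections conflict.
3. **Treatment-related grade 4 event after the DLT observation period, delay of 2 to 4 weeks, resolved within 3 weeks.** Section 6.2.2.1.2 allows resumption. Under 6.2.2.1.3 the answer depends on the exception. If it refers to the types of event exempted in 6.2.1.4, restart is barred. If it refers to the onset window, a later event is not a DLT and restart is not barred. The text does not say which, so this is an ambiguity and not a flat contradiction.
4. **First grade 3 DLT recovering within 3 weeks, an exempt grade 4 event, or a grade 5 event.** There is no conflict over restart.

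The sign-off difference cuts across these cases: GSO agreement is a condition in 6.2.2.1.1 only.

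On precedence, 6.2.2.1.1, 6.2.2.1.2 and 6.2.2.1.3 all refer to 6.8.1, 6.8.3 and 6.8.4 for CRS, neurological events and pituitary dysfunction. Neither 6.2.2.1.1 nor 6.2.2.1.2 refers to 6.2.2.1.3, and none of the three says which prevails.

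**The case against.** The best answer is that the sections can be read together. They stand under one heading and divide the work: dose level, length of delay, eligibility to restart. Section 6.2.2.1.3 itself first permits resumption after a DLT and then lists exclusions, so its list can be taken as a limit on the other two. Section 6.8.4 also sends the reader to 6.2.2.1.3 for restarting, and 6.2.2.1.1 grants only an option with several conditions. This reading is plausible, but it has to be supplied by the reader. Section 6.2.2.1.1 is itself worded as a specific exception for subjects with a DLT and benefit, so a site could as reasonably treat it as the special rule.

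The objection to the 6.2.2.1.2 limb largely stands. That rule applies after the DLT observation period, and severe or life-threatening can be read as grade 3, exempt grade 4 or later events. Only the unclear exception remains.

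Three stronger readings are tempting and are not supported:

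- **Section 7.2.** A reader might infer that its bar on "treatment related adverse events of CTCAE grade 4 at the current dose at the time of progression" presupposes re-dosing after a barred grade 4 event. The same list requires that no other discontinuation criterion is met and excludes unacceptable toxicity at any dose. Grade 4 at an earlier dose can also be an exempt event, which 6.2.2.1.3 does not bar.
- **A count from Table 9-3.** A reader might apply its 10% to 30% rates to the expansion cohort. Those are hypothetical true rates for all grade 4 or higher treatment-related events, including exempt events and events with their own rule, and they ignore the conditions in 6.2.2.1.1.
- **Progression and response follow-up.** A reader might infer that the choice decides how much is accrued. Section 8.1.4 continues imaging after discontinuation for reasons other than confirmed progression, within stated limits, and SAP Appendix C does not censor at treatment discontinuation.

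**Conclusion.** The concern holds in a limited form. Sections 6.2.2.1.1 and 6.2.2.1.3 disagree for a non-exempt, treatment-related grade 4 DLT that recovers in a subject with benefit, for a grade 3 DLT that recovers after 3 weeks, and on GSO agreement. Section 6.2.2.1.2 adds an ambiguity about the DLT exception.

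The number of subjects is not in the documents. The conflict is confined to events without their own rule, so outside CRS, neurologic events, pituitary dysfunction, neutropenia (Section 6.8) and hepatotoxicity (Section 11.7). Hypersensitivity is an example of what remains: Section 8.4.8.2 gives no graded restart rule.

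Timing narrows it further. Enrollment ended in January 2023 (Section 4.1) and the current protocol is dated 05 June 2024, at least 16 months later. The DLT window runs from the first dose and its length is not legible. Assuming that it is shorter than 16 months and that dosing followed soon after enrollment, subjects still on tarlatamab cannot have a new DLT by onset. For them the open question is a later grade 4 event. Section 6.2.2.1.1 can reach it as another intolerable event, and 6.2.2.1.3 bars restart or not according to how its exception is read.

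This is a safety-relevant clarification. It does not undermine the trial's analyses.

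**What to change.** Reconcile 6.2.2.1.1, 6.2.2.1.2 and 6.2.2.1.3 so that the grade, time and sign-off conditions for resuming tarlatamab agree. State which section governs where more than one applies. State whether the exception in the grade 4 bullet of 6.2.2.1.3 depends on the type of event or on onset within the DLT window. The medical team must decide which rule applies; this review takes no view on that.

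The cost is a protocol clarification letter, or a few sentences in the next amendment. No planned analysis has to change.

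### After an initial grade 3 non-febrile neutropenia, Protocol Table 6-8 and Section 6.2.2.1.3 give opposite restart instructions, and the third do-not-restart bullet lacks the return-to-baseline alternative used elsewhere

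*Protocol*

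**What the plan says.** Four parts of the protocol govern when tarlatamab may be restarted after a grade 3 event.

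- **Section 6.2.2.1.3, resume sentence.** Dosing may resume if the toxicity falls to grade 1 or below "or return to subjects' baseline values within 3 weeks", with the agreement of the investigator and the medical monitor.
- **Section 6.2.2.1.3, do-not-restart list (treatment-related events).** The third bullet is "Grade 3 adverse event(s) that do not recover to grade ≤ 1 within 3 weeks". The fourth bars restart after a recurring grade 3 event but exempts, among others, "recurrent non-febrile grade 3 neutropenia which resolves with supportive care to grade ≤ 1 or returns to subjects' baseline values within 3 weeks".
- **Section 6.2.2.1.2, after the DLT period.** For delays of up to 2 weeks the subject "should resume the treatment as soon as possible if deemed safe by the investigator". For delays of 2 to 4 weeks due to severe or life-threatening treatment-related events, "the subject can resume treatment if the toxicities resolve to grade ≤ 1 or return to subjects' baseline values within 3 weeks", again with investigator and medical monitor agreement. Longer delays for such events end treatment.
- **Table 6-8, grade 3 non-febrile neutropenia.** Interrupt until grade 2 or lower, then resume at the same dose, at least 72 hours after the event was first seen. Stop permanently if an initial event has not come down to grade 2 or lower in 3 weeks.

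Section 2.3.3.1 (Table 2-1) and Section 6.8.5 both say that the neutropenia interruption and stopping rules are in Table 6-8. The closing lines of the dose-modification sections do not. For CRS, neurological and pituitary events, Section 6.2.2.1.3 ends "please see Sections 6.8.1, 6.8.3, and 6.8.4 respectively for guidelines for dose adjustment" and Section 6.2.2.1.2 ends "please see Sections 6.8.1, 6.8.3, and 6.8.4 respectively for guidelines for dose delays". Section 6.2.2.1.1 closes in the same way. None names Section 6.8.5.

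**The concern.** Whether to restart a T-cell engager or stop it for good is a safety decision, and the site needs one answer. For an initial grade 3 non-febrile neutropenia the protocol has two thresholds over the same 3 weeks: grade 2 in Table 6-8 and grade 1 in the third bullet. A subject who settles at grade 2 may restart under one and must not under the other.

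The baseline question is separate. The third bullet asks every subject to reach grade 1 or below, including those admitted with a value already above grade 1. The resume sentence just above it, the 2-to-4-week rule and the fourth bullet all accept a return to baseline. As written, a recurrent grade 3 neutropenia has a baseline alternative that a first grade 3 event lacks.

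At stake are the safety of subjects still on tarlatamab and the reading of discontinuations for adverse events. SAP Section 9.6.2 tabulates these and lists neutropenia as an event of interest.

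**Working it through.** There is no planned figure to reproduce. The check applies each rule to a defined subject. Both examples assume that the event falls after the DLT period, that day 0 is both onset and the due date of the next dose, and that a severe event means grade 3.

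**Example 1: neutropenia.** An initial treatment-related grade 3 non-febrile neutropenia in a subject with baseline at grade 1 or below. It reaches grade 2 on day 16 and is still grade 2 on day 22, with restart pending.

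| Rule | Test | Answer on day 22 |
|---|---|---|
| Table 6-8 | grade ≤ 2 reached on day 16, and 16 ≤ 21; day 22 is past 72 hours (day 3) | restart at same dose permitted |
| 6.2.2.1.3, third bullet | grade ≤ 1 not reached by day 21 | restart barred |
| 6.2.2.1.2, 2-to-4-week rule | delay of 22 days, 14 < 22 ≤ 28; grade 2 is neither ≤ 1 nor baseline | conditions for restart not met |

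The disagreement does not depend on waiting until day 22. On day 16 the delay already exceeds 14 days, so Table 6-8 permits restart while the conditions of 6.2.2.1.2 are unmet. The third bullet adds an outright bar once 3 weeks have passed. For delays of up to 2 weeks, 6.2.2.1.2 sets no grade threshold and is compatible with Table 6-8.

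**Example 2: baseline above grade 1.** Inclusion criterion 107 admits AST/ALT < 5 x ULN with liver involvement. Table 6-2 puts 3 to 5 x ULN at grade 2 and 5 to 20 x ULN at grade 3. Take a baseline ALT of 4 x ULN (grade 2). It rises to 6 x ULN (grade 3, treatment-related), stays above 5 x ULN for 12 days, and is back at 4 x ULN on day 17. Restart is pending on day 22.

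- Table 11-3 is not triggered: 6 < 8, and 12 days < 14 days. This assumes no hepatitis symptoms, normal bilirubin, INR and ALP, and monitoring kept.
- 6.2.2.1.2: delay of 22 days, 14 < 22 ≤ 28, and return to baseline on day 17 ≤ 21. Restart permitted.
- 6.2.2.1.3, third bullet: still grade 2 after 3 weeks. Restart barred.

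For an event on the withhold list of 6.2.2.1.3, the resume sentence gives the same permissive answer as 6.2.2.1.2, so the conflict then lies within one section.

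**The case against.** The strongest reply is that the specific rule governs. Sections 2.3.3.1 and 6.8.5 place the neutropenia stopping rules in Table 6-8, and the DLT definition in 6.2.1.4 also refers to Section 6.8.5 for neutropenia management. A table written for one event would ordinarily prevail over a general bullet. That is probably the intention, and it points to the right fix. It does not settle the text. The three dose-modification sections defer by name to 6.8.1, 6.8.3 and 6.8.4, so a reader may take the omission of 6.8.5 as deliberate. Section 6.2.2.1.3 also sets a neutropenia standard of its own in the fourth bullet. That bullet is only supporting evidence, because it concerns recurrent events while the discontinuation column of Table 6-8 concerns the initial one.

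A reader might infer that Section 6.2.2.1.1 also conflicts with Table 6-8 from the first 72 hours, since it speaks of resuming at grade 0 to 1 with no baseline alternative. The documents do not establish this. Both recovery sentences there follow text on dose reduction and can be read as covering restart at a reduced dose, whereas Table 6-8 restarts grade 3 neutropenia at the same dose. Whether there is a conflict depends on that reading.

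It is also fair that the examples are chosen cases, that in Example 2 no cited rule forced the delay, and that the medical monitor would see many of them. But the grade 3 row of Table 6-8, unlike the grade 4 row, does not ask for discussion with the medical monitor before restart.

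**Conclusion.** The contradiction holds for an initial treatment-related grade 3 non-febrile neutropenia that recovers only to grade 2: Table 6-8 permits restart, the third bullet bars it after 3 weeks, and the 2-to-4-week rule withholds it unless grade 2 is the subject's baseline. The missing baseline alternative in the third bullet is a second, smaller inconsistency, confined to subjects whose baseline exceeds grade 1.

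The size is modest. Protocol Section 4.1 states that enrollment ended in January 2023, so the effect is on subjects still receiving tarlatamab and on how discontinuations for adverse events are read. The documents give no basis for a share of affected subjects. Section 2.2.2.3 reports grade ≥ 3 neutropenia in 11.8% of Part A2 monotherapy subjects of the first-in-human study. That shows the event occurs, but not how often recovery stops at grade 2.

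Two further inferences should be resisted. One is a conflict window of fixed length, such as day 21 to day 28. The bullet counts weeks of event recovery, while the 4-week limit in 6.2.2.1.2 counts weeks of dosing delay. The two clocks coincide only if onset falls on a planned dose day, as the examples assume. The other is an effect on the primary results. The DLT definition has its own neutropenia criterion, and the DLT analysis, the RP2D and the SAP methods do not change.

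**What to change.** In the next protocol amendment:

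1. Add Section 6.8.5 / Table 6-8 to the closing cross-references of 6.2.2.1.1, 6.2.2.1.2 and 6.2.2.1.3. This follows the protocol's own statement of where the neutropenia stopping rules are. It also settles the 2-to-4-week rule and the reading of 6.2.2.1.1 for these events.
2. Except initial non-febrile neutropenia managed under Table 6-8 from the third do-not-restart bullet. Febrile neutropenia stays under the bullet, since the table does not cover it.
3. Add the return-to-baseline alternative to the third bullet, in the terms of the resume sentence above it.

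The cost is three cross-references, one exception and one added phrase. Because a stopping rule changes, it needs an amendment rather than a clarification letter, but it can go in with other changes. Neither the SAP nor data collection needs revision.

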6.2.2.1.4 Criteria to Pause Enrollment

At any point during the study, enrollment will be paused at the occurrence of 2 or more of the same grade 4 or one or more grade 5 investigational product-related adverse events. The DLRT will be reconvened to review the safety data and determine appropriate next step that may include but not limited to implementing safety/toxicity management, informing health authorities, voluntarily putting the clinical trial on hold, or proceeding with enrollment. (Note: following occurrence of an enrollment pause and DLRT review, a subsequent enrollment pause will occur at the occurrence of 2 or more new grade 4 or 1 more grade 5 investigational product-related adverse events; additionally, if a pause and a DLRT has already occurred and the appropriate

Protocol Number: 20200439

Date: 05 June 2024 Page 62 of 176

safety/toxicity management for grade 4 adverse events have already been implemented a subsequent enrollment pause may not occur.)

6.2.2.2 Amgen Investigational Product: AMG 404

